To characterize the efficacy of efgartigimod PH20 SC in the treatment of participants with BP	4. Proportion of participants who are in CR while receiving efgartigimod PH20 SC or placebo and have been receiving minimal OCS therapy for ≥8 weeks at week 36. (Minimal OCS therapy is defined as ≤0.1 mg/kg/day of prednisone [or an equivalent dose of another OCS].)						
5. To evaluate the effect of efgartigimod PH20 SC on pruritus in participants with BP	Changes from baseline in the 24-hour average itch score from the Itch NRS						
Other Secondary							
To further characterize the overall efficacy of efgartigimod PH20 SC in the treatment of participants with BP	 Proportion of participants who achieve an IGA-BP score of 0 or 1 while receiving efgartigimod PH20 SC or placebo and have been off OCS therapy for ≥8 weeks at week 36 Proportion of participants who achieve an IGA-BP score of 0 or 1 while receiving efgartigimod PH20 SC or placebo at any time through week 36 Changes from baseline in the BPDAI activity score Time to achieve the following: CDA CR CR while on minimal OCS therapy for ≥8 weeks CR while off OCS therapy for ≥8 weeks Relapse Cumulative OCS dose for the participant at the time points where they exhibit the following: CDA CR CR while on minimal OCS therapy for ≥8 weeks CDA CR CR while on minimal OCS therapy for ≥8 weeks CR while off OCS therapy for ≥8 weeks Relapse 						

Table 4: Part B Objectives and Endpoints (Continued)

Objectives	Endpoints
Other Secondary (continued)	
To further characterize the overall efficacy of efgartigimod PH20 SC in the treatment of participants with BP (continued)	 Changes from baseline in the 24-hour worst itch score from the Itch NRS Proportion of participants who receive rescue therapy before week 36
To assess the safety and tolerability of efgartigimod PH20 SC administered to participants with BP	Incidence and severity of TEAEs, AESIs, and SAEs Vital sign measurements, physical examinations, ECGs, and clinical laboratory safety evaluations
To assess glucocorticoid-associated morbidity and evaluate the impact of efgartigimod PH20 SC in reduction of glucocorticoid toxicity	 The Aggregate Improvement Score (AIS) from the GTI The Cumulative Worsening Score (CWS) from the GTI The GTI Specific List (GTI-SL)
To evaluate the effects of efgartigimod PH20 SC on the QoL of participants with BP	 EQ-5D-5L scores over time DLQI scores over time ABQoL scores over time

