8.3.9. Additional Safety Assessment – the Glucocorticoid Toxicity Index

As an additional assessment of the impact of glucocorticoid morbidity, the GTI v2.0 will be assessed at the visits listed in the SoA (Table 1). The GTI v2.0 is a complementary scoring system to the overall report of AEs that are considered related to glucocorticoids by investigators during interventional studies. It also enables the monitoring of long-term tolerability of glucocorticoids during their prolonged use during clinical practice.³⁹

The GTI v2.0 consists of the following 2 instruments:

The Composite-GTI (C-GTI), which serves as a primary instrument intended to capture
toxicities that are likely due to glucocorticoid exposure. The C-GTI has 9 functional
domains: BMI, glucose control, blood pressure, lipid metabolism, bone mineral density,
muscle strength, skin toxicity, neuropsychiatric effects, and infection. Each domain
includes several weighted items that correspond to varying degrees of glucocorticoid
toxicity.

Note: the bone mineral density domain will not be used in this study, because it is typically excluded from studies <1 year in duration, because bone densitometry is not sufficiently reliable in measuring changes over shorter durations.³⁹

Two analytical scores are generated from the weighted C-GTI items: the Cumulative Worsening Score (CWS) and the AIS. The CWS is designed to assess cumulative glucocorticoid toxicity, while the AIS can be used to assess whether a new therapy is effective in reducing glucocorticoid toxicity over time. Together, the CWS and AIS provide complementary information about the ability of an investigational agent to reduce overall glucocorticoid toxicity.

• The Specific List of the GTI (GTI-SL) captures well-known glucocorticoid-related side effects. This non-weighted instrument provides additional information for the domains

most affected by glucocorticoid use during the participant's course of treatment. It comprises 11 domains (9 of which are shared in common with the C-GTI) and 23 items.

Note: for the reason mentioned above, the GTI-SL item covering bone mineral density decrease (part of the Bone Health domain; Table 15) will not be used in this study.

The tabular components of the modified GTI are presented in Section 10.12.

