9.3.3.2. Analysis of Other Secondary Endpoints

Other secondary endpoints (which are not subject to alpha control) are listed in Table 3 and Table 4; these have been selected to evaluate other aspects of the effects of efgartigimod PH20 SC in participants with BP, including its safety/tolerability, health impact, QoL, PK/PD, and immunogenicity. Additionally, this study includes endpoints to evaluate whether participants (and/or their caregivers) can competently (self-)administer efgartigimod PH20 SC.

These endpoints are not subject to multiplicity correction, and their analyses are purely descriptive.

Time to CDA and CR will be tested using a stratified Gehan-Wilcoxon test. The other time to event endpoints will be tested using a stratified log-rank test.

All continuous secondary endpoints (such as the C-GTI and QoL instruments) will be analyzed using a mixed-effect model for repeated measures.

Descriptive statistics will be provided for self-administration training, PD (total IgG serum levels and the anti-BP180 and anti-BP230 antibodies), incidence of ADA and NAb against efgartigimod, and incidence of antibodies and NAb produced against rHuPH20. Data for efgartigimod serum concentrations will be summarized. Total IgG serum levels and autoantibody data will be summarized in absolute values, change from baseline, and percent reduction from baseline over time. Population PK/PD analysis may be performed based on the PK and PD data and reported separately.

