Descriptive statistics on absolute values and changes from baseline for EQ-5D-5L VAS score, DLQI score and Total ABQOL score will be calculated per time point.

The same MMRM model as for the itch NRS score will be applied to analyse these changes from baseline but using a standard unstructured covariance matrix (UN) since there are only 3 post-baseline visits during the treatment-phase.

17) C-GTI: Composite Glucocorticoid Toxicity Index comprises the Aggregate Improvement Score (AIS) and the Cumulative Worsening Score (CWS) (health impact of GC) and is derived at baseline, Week 12, Week 26, and Week 36/ETD/ESD. AIS and CWS are calculated for the first 12 weeks, 26 weeks, and 36 weeks period and overall (period till last post-baseline assessment). Details of AIS and CWS derivations are specified in appendix 9.2.

A 'treatment policy' approach will be applied by ignoring ICEs. For participants who received rescue therapy, only assessments prior to or on the start date of rescue therapy will be considered.

Descriptive statistics will be provided for the C-GTI scores AIS and CWS; treatment groups will be compared at each visit using the same ANCOVA model as for the NCOD analysis. C-GTI will be analysed on complete cases: i.e., participants with C-GTI assessment at baseline and at least one post-baseline visit. Participants where first post-baseline GTI improvements/worsening have not been obtained with respect to the baseline moment but with respect to a later moment (i.e., no GTI assessment at baseline visit) are excluded from analyses and are only listed.

Kaplan-Meier curves will be created for all 'time to event' endpoints.

[figure not shown]
Separate listings will be created for all 'time to event' endpoints, for lesion assessments, for BPDAI assessments and scores, for ABQOL, EQ-5D-5L and DLQI data, for calculated C-GTI scores and for complementary GTI specific list (GTI-SL).

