ARGX-113-2009	Final and Interim Analysis	Final 4.0 of 04NOV2024

TL

TL

14.2.1.3.5.1	Itch NRS 24-hour Worst Score: Descriptive Statistics of Actual Values and Changes from Baseline by Visit - FAS	FAS
14.2.1.3.5.2	Itch NRS 24-hour Worst Score: MMRM on Changes from Baseline - FAS	FAS
14.2.1.3.6.1	Proportion of Participants with Rescue Therapy before Week 36: Cochran-Mantel-Haenszel - FAS	FAS
14.2.1.3.7.1	C-GTI: Descriptive Statistics of CWS and AIS - FAS	FAS
14.2.1.3.7.2	C-GTI: ANCOVA on CWS and AIS - FAS	FAS
14.2.1.4.1.1	ABQOL: Frequency Tabulation of 17 Items by Visit - FAS	FAS
14.2.1.4.1.2	ABQOL: Descriptive Statistics of Actual Values and Changes from Baseline by Visit in ABQOL Total Score - FAS	FAS
14.2.1.4.1.3	ABQOL: MMRM on Changes from Baseline in ABQOL Total Score - FAS	FAS
14.2.1.4.2.1	EQ-5D-5L: Frequency Tabulation of 5 Dimensions by Visit - FAS	FAS
14.2.1.4.2.2	EQ-5D-5L: Descriptive Statistics of Actual Values and Changes from Baseline by Visit in VAS Score - FAS	FAS
14.2.1.4.2.3	EQ-5D-5L: MMRM on Changes from Baseline in VAS Score - FAS	FAS
14.2.1.4.3.1	DLQI: Frequency Tabulation of 10 Items by Visit - FAS	FAS
14.2.1.4.3.2	DLQI: Descriptive Statistics of Actual Values and Changes from Baseline by Visit in DLQI Score - FAS	FAS
14.2.1.4.3.3	DLQI: MMRM on Changes from Baseline in DLQI Score - FAS	FAS
PHARMACOKIN	ETICS	
14.2.2.1	Descriptive Statistics of Efgartigimod Serum Concentration over Time	PK
PHARMACODY	NAMICS	
14.2.3.1	Descriptive Statistics of Actual Values, Changes from Baseline and Percent Changes from Baseline in Total IgG Level by Visit	PD
14.2.3.2	Descriptive Statistics of Actual Values, Changes from Baseline and Percent Changes from Baseline in Total IgG Level by Visit - by Subgroups	PD

SGS	Statistical Analysis Plan	
ARGX-113-2009	Final and Interim Analysis	Final 4.0 of 04NOV2024

TL

14.2.3.3	Descriptive Statistics of Actual Values, Changes from Baseline and Percent Changes from Baseline in Total by Visit	PD
14.2.3.4	Descriptive Statistics of Actual Values, Changes from Baseline and Percent Changes from Baseline in Total by Visit - by Subgroups	PD
14.2.3.5	Descriptive Statistics of Actual Values, Changes from Baseline and Percent Changes from Baseline in anti- BP180 and anti-BP230 Antibodies by Visit	PD
14.2.3.6	Descriptive Statistics of Actual Values, Changes from Baseline and Percent Changes from Baseline in anti- BP180 and anti-BP230 Antibodies by Visit - by Subgroups	PD
IMMUNOGENIC	ITY	

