9.2 GTI: DERIVATION OF CWS AND AIS

9.2.1 Allocate weights

Weights per item are attributed as specified below. GTI at Wx is evaluated versus previous GTI assessment. The first time point is referred to as *start (or previous)* and the second time point within each comparison is referred to as *follow-up (or current)*.

Increase, decrease or no change in medication intake compared to previous assessment are checked in the GTI assessment. A missing evaluation, including for external data, will be considered as no change with weight=0.

External GTI data (i.e., LDL/HbA1c/BP and BMI) are allocated to a GTI assessment based on dates. The last available value of these external data since previous GTI assessment will be used.

Changes from severe to moderate do not have any impact on calculation of CWS/AIS. Severe outcome on an item however is captured on the specific list (SL).

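### GTI-SL is a named secondary endpoint and carries most severe steroid-toxicity outcomes within the GTI, yet the SAP plans only a participant listing for it and no summary by arm.

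*SAP*

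**What the plan says.** **Endpoint.** Protocol Table 3 (Part A, secondary) and Table 4 (Part B, other secondary) set three endpoints against the objective on glucocorticoid morbidity: AIS, CWS and "The GTI Specific List (GTI-SL"). SAP 4.1.1 repeats all three as the measures of the health impact of glucocorticoid use.

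**Instrument.** Protocol 8.3.9 describes GTI-SL as non-weighted: "It comprises 11 domains (9 of which are shared in common with the C-GTI) and 23 items". The bone mineral density item is not used. The schedule of activities collects the GTI at baseline, weeks 12, 26 and 36, and at early treatment or study discontinuation.

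**Promised analysis.** Protocol 9.3.3.2 covers the other secondary endpoints, including health impact: "These endpoints are not subject to multiplicity correction, and their analyses are purely descriptive".

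**Planned analysis.** SAP 4.1.4 item 17 states: "Descriptive statistics will be provided for the C-GTI scores AIS and CWS; treatment groups will be compared at each visit". The two GTI tables in SAP 8.1 are "C-GTI: Descriptive Statistics of CWS and AIS - FAS" (14.2.1.3.7.1) and "C-GTI: ANCOVA on CWS and AIS - FAS" (14.2.1.3.7.2). GTI-SL appears only among the listings: "for calculated C-GTI scores and for complementary GTI specific list (GTI-SL").

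**Role of GTI-SL.** SAP 9.2.1 says that a move from severe to moderate does not change CWS or AIS, and adds: "Severe outcome on an item however is captured on the specific list (SL").

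**The concern.** One of the three endpoints for a stated objective has no planned summary by arm. A listing shows individual rows. It gives no counts, percentages or denominators, so it is less than a descriptive analysis.

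The omitted endpoint is also not a duplicate of the other two. By the SAP's own account, the weighted scores mostly stop distinguishing toxicity above moderate and leave the severe level to the specific list. If that list is never summarised, an imbalance in severe steroid toxicity between arms could go unreported under the objective meant to describe it. Anyone who wanted the comparison would have to count from the listing after unblinding, with no agreed denominator, time points or rule for assessments after rescue therapy.

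**Working it through.** No sample size, power or alpha figure bears on this point. The check traces GTI-SL through both documents and reads the C-GTI weights for a moderate/severe split.

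**1. Planned GTI displays (SAP 4.1.4, SAP Table 4, 8.1, 8.2)**

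| Endpoint | Summary table by arm | Model | Listing |
|---|---|---|---|
| AIS | 14.2.1.3.7.1 | ANCOVA, 14.2.1.3.7.2 | 16.2.6.10 |
| CWS | 14.2.1.3.7.1 | ANCOVA, 14.2.1.3.7.2 | 16.2.6.10 |
| GTI-SL | none | none | 16.2.6.11 |

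SAP Table 4 has a C-GTI row and no GTI-SL row. SAP 2.4.3 produces listings for Parts A and B separately, so the pooled analysis has no GTI-SL display at all. SAP 6.1 records three changes from the protocol (NCOD weight, intercurrent medications, death), and none concerns GTI-SL. By contrast, the individual items of ABQoL, EQ-5D-5L and DLQI all get frequency tables by visit (14.2.1.4.1.1, 14.2.1.4.2.1 and 14.2.1.4.3.1).

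**2. Do CWS and AIS separate severe from moderate? (SAP 9.2.1.1 to 9.2.1.9)**

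- Myopathy: moderate and severe are one tier. None to mild is 9 and mild to moderate/severe is 54; 9 + 54 = 63 for none to either level.
- Skin: 8 + 18 = 26 for none to moderate or severe. The grading table gives a severe grade for acneiform rash, atrophy/striae and erosions/tears/ulcerations, but not for easy bruising or hirsutism. The merging therefore affects 3 of 5 subitems.
- Neuropsychiatric: 11 + 63 = 74. Mania, cognitive impairment and depression have a severe grade; insomnia does not. The merging affects 3 of 4 subitems. Psychosis and glucocorticoid-induced violence are taken from the specific list and also score 74.
- BMI, glucose, blood pressure and lipids: nothing is scored above the top worsening weight (36, 44, 44 and 30). A hypertensive emergency or PRES scores 44, the same as moderate worsening.
- Infection: Grade 3 to 5 or complicated zoster is a category of its own, apart from lower grades. This is the one domain where the split exists.

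For example, a participant going from no depression to moderate and another going from none to severe each add 74 to CWS, a difference of 74 − 74 = 0.

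**3. Content outside the C-GTI.** GTI-SL has 11 domains, 9 of them shared: 11 − 9 = 2 domains with no planned GTI table of any kind.

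**4. Adverse-event tables by arm (SAP 5.1.3, 8.1)**

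- 14.3.1.7: Grade 3 or higher, any cause.
- 14.3.1.8: Grade 3 or higher, related to treatment. Prednisone relatedness is a separate attribute in SAP 5.1.2.
- 14.3.1.9: prednisone-related, any grade.
- 14.3.1.6: prednisone-related and serious. Protocol 10.3.3 warns that severe and serious are different classifications.

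No table combines Grade 3 or higher with prednisone-related.

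**The case against.** The strongest reply has four parts.

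*Severe toxicity is visible elsewhere.* A reader might infer that GTI-SL is the only place where severe is separated from moderate. The documents do not support that. The infection domain makes the split, adverse events are CTCAE-graded and assessed for relation to corticosteroids, and the tables above are by arm. This stands as partial cover. The missing cross of grade with steroid attribution remains, and protocol 8.3.9 presents the GTI as complementary to adverse-event reporting, so those tables do not replace the endpoint.

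*Some GTI-SL content does reach a comparison.* A reader might also infer that no between-arm result can ever exist. That goes too far. Psychosis and violence enter CWS and AIS, and the listing is ordered by treatment, so counts could be made later. But those two items carry the same 74 points as a moderate event and cannot be identified within the score, and a later count is not a planned analysis.

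*The protocol's promise is general.* Protocol 9.3.3.2 goes on to name particular outputs for descriptive statistics, and GTI-SL is not among them. That is correct, but the general sentence still covers health-impact endpoints, and SAP 4.1.1 places GTI-SL there.

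*The item content is not visible.* Protocol Table 15 cannot be read in the public copy, so the number of items that are severe versions of C-GTI items cannot be counted. That stands, and it limits how precisely the loss can be sized.

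**Conclusion.** The gap is real and small. One of three named endpoints for the glucocorticoid-toxicity objective has a listing and no summary by arm in Part A, Part B or the pooled data. This falls short of protocol 9.3.3.2 and is not declared in SAP 6.1. Apart from infection, GTI-SL is the GTI component to which the SAP assigns severe outcomes. The affected scores are myopathy, three skin subitems and three neuropsychiatric subitems, not every item in those domains.

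The conclusion rests on the SAP's own statement in 9.2.1 and its grading tables, since the item list itself is not legible. It is not that severe steroid toxicity goes unreported, only that this endpoint's share of it has no planned summary. The endpoint is outside alpha control, so no primary or key secondary conclusion changes.

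**What to change.** Add one descriptive table to SAP 4.1.4 item 17 and to the list in 8.1, after 14.2.1.3.7.2. For each GTI-SL item, give n (%) per arm present at baseline, and newly present by weeks 12, 26 and 36 and overall. Define newly present as absent at baseline and present at any later assessment up to that time point. Produce it for Part A, Part B and pooled. Use item 17's existing rules: main intercurrent events ignored, and only assessments up to the start of rescue therapy counted. State the denominator at each time point.

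No test is needed, and no pooled at-least-one-item outcome: neither document defines one, and it would mix items of unequal weight. If the sponsor prefers to keep listing-only reporting, SAP 6.1 should say so and give the reason, though the endpoint would then still lack its summary.

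The cost is one extra descriptive table from data already collected, with no effect on alpha or sample size.

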4.1.5 Fixed-Sequence testing procedure

The fixed-sequence testing procedure will only apply for the analysis of study Part B.

To control the type I error for the primary and secondary endpoints (alpha controlled), the primary efficacy endpoint will be tested at the 5% 2-sided alpha level and will act as gatekeeper for the testing of the key secondary endpoints. The primary endpoint and secondary endpoints will be tested in a strict hierarchical order as per the algorithm of section 1.4.3.2 to control the type I error.

The individual per-endpoint tables will only show unadjusted p-values. A fixed-sequence testing procedure table will be produced. This table will show both unadjusted p-values and p-values adjusted for multiplicity. For a given endpoint, the adjusted-for-multiplicity p-value is calculated as the maximum between its unadjusted p-value and the highest of all unadjusted p-values tested before.

- Primary endpoint: the proportion of participants who are in CR while receiving efgartigimod PH20 SC or placebo and have been off OCS therapy for ≥8 weeks at week 36 using a 'composite strategy' approach
- Secondary endpoints:
 - NCOD using 'while on treatment strategy' approach
 - Proportion of participants achieving IGA-BP score of 0 while receiving efgartigimod PH20 SC or placebo and have been off OCS therapy for ≥8 weeks at week 36 using a 'composite strategy' approach
 - Proportion of participants achieving control of disease activity (CDA) while receiving efgartigimod PH20 SC or placebo and remain free of relapse through week 36 using a 'composite strategy' approach
 - Proportion of participants achieving CR while receiving efgartigimod PH20 SC or placebo and have been receiving minimal OCS therapy for ≥8 weeks at week 36 using a 'composite strategy' approach
 - Change from baseline to week 36 in the 24-hour average Itch NRS score using a 'treatment policy' approach

4.1.6 Subgroup analyses for efficacy

Subgroups are defined based on the following categorizing factors:

- Disease history (newly diagnosed versus relapsing)
- Disease severity as per IGA-BP at screening (moderate versus severe)
- BPDAI activity score at baseline: <20, 20-56, >56
- Geographical region (Asia, North America, EU region+UK, Rest of world)
- Sex at birth
- Age at informed consent (18 <65, 65 <75, 75 <85, >=85)
- BMI at screening (Underweight: < 18.5 kg/m², Normal weight: 18.5 -< 25 kg/m², Overweight: 25 -< 30 kg/m² Obese: >= 30 kg/m²)
- Race (Asian, Black or African American, White, Other)

Subgroup analyses will be performed on the primary and key secondary efficacy endpoints.

SGS	Statistical Analysis Plan	
ARGX-113-2009	Final and Interim Analysis	Final 4.0 of 04NOV2024

Following table summarizes the analyses:

Table 4: Summary of (subgroup/supplementary) analyses

[figure not shown]
Subject level variable	Estimand	Estimator
CRoff at week 36	Composite	CMH ^{1,p,s} Logistic regression
	Treatment policy	MI + CMH
NCOD	While on treatment	ANCOVA ^{2,p,s}
	Treatment policy	ANCOVA
IGA-BP score of 0 at week 36 while off OCS therapy for ≥8 weeks	Composite	CMH ^{2,p,s}
CDA and remain free of relapse through week 36	Composite	CMH ^{2,p,s}
CRmin at week 36	Composite	CMH ^{2,p,s}
Itch NRS 24-hour average score	Treatment policy	MMRM ^{2,p,s}
IGA-BP score of 0 or 1 at week 36 while off OCS therapy for ≥8 weeks	Composite	CMH
IGA-BP score of 0 or 1 at any time through week 36	Composite	CMH
BPDAI activity and total score/Itch NRS worst score	Treatment policy	MMRM
Time to CDA/CR	Composite	Gehan-Wilcoxon
Time to relapse from CDA/CR/CRoff	Treatment policy	Log-rank
Other time to event	Composite	Log-rank
NCOD for subperiods	While on treatment	ANCOVA
Received rescue therapy before week 36	Treatment policy	CMH
QoL	Treatment policy	MMRM
C-GTI	Treatment policy	ANCOVA

¹ Primary endpoint

² Key secondary endpoint for study Part B

^p Also analysis on PP analysis set will be performed.

s Also subgroup analyses will be performed. No inferential statistics will be calculated for the subgroup analyses.

